10 INVESTIGATIONAL AGENTS

Bupropion SR tablets, 150 mg, and matching placebo will be supplied by Murty Pharmaceuticals, Inc., (Lexington, KY) under a contract with NIDA. GSK's Zyban (bupropion) SR tablets, 150 mg, will be film-coated by Murty Pharmaceuticals to mask information on tablet surface. Matching placebo will be manufactured by Murty Pharmaceuticals. Data show that the film coating has negligible effect on the dissolution of Zyban SR tablets.

10.1 DISPENSING INVESTIGATIONAL AGENTS

Murty Pharmaceuticals will distribute the investigational agents packaged in HDPE bottles with child-resistant closure to investigators or designated Research Pharmacists at the clinical sites for dispensing to subjects. Used and unused investigational agents will be collected and inventoried each week and a study agent compliance CRF will be completed.

Investigational agents will be dispensed to subjects once per week at the first clinic visit of the week. Investigational agents will be distributed directly to the subject by the investigative staff

depending upon local site procedures. The subject will be thoroughly instructed on how to administer investigational agents.

Subjects will be instructed to store the medication at room temperature without exposure to direct sunlight. Subjects will be instructed to consume the morning dose between 8:00 and 10:00 a.m. and the evening dose between 4:00 and 6:00 p.m. The exact time of the morning and evening doses may vary across patients depending on their schedules, but should be maintained constant for a particular individual. Administration of the daily dose in divided doses of maximum 150 mg twice daily, at least 8 hours apart, should minimize the risk of seizures. Unused investigational agents will be collected and inventoried each week.

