10.2 LABELING

Investigational agents will be packaged in HDPE bottles with child-resistant closure with a 10day supply. The bottles will be labeled by Murty Pharmaceuticals with the drug name ("bupropion/placebo"), the random dose code, and the following statement – Caution: New Drug – limited by federal law to investigational use. Bottles will be distributed to investigational sites. When a subject is assigned to treatment, the local site research pharmacist, investigator or designee, will label the appropriate bottle based on the random dose code assigned to the patient with the following information: subject's study identification number, subject's letter identification code, the words "Study Week X", where X is the study week number (i.e., 1 through 12), and the number of tablets to take per day (i.e., 1 tablet on days 1-3 and days 82-84 and 2 tablets on days 4-81).

The label will also include a warning indicating that this medication should be kept out of children's reach. Special labels will be prepared for each site indicating the local Principal Investigator's name and 24-hour emergency telephone number.

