10.5 SAFETY CONSIDERATIONS

One of the potentially most serious adverse effects of bupropion is reduction in the seizure threshold (Johnston *et al.*, 1991, Settle, 1998, Storow, 1994). Bupropion is contraindicated in

patients with a seizure disorder or a predisposing factor for seizures (e.g., cranial trauma history, current seizure disorder, concomitant use of drugs that lower seizure threshold). However, the relative risk of seizures with various antidepressants, including bupropion, has not been clearly defined and the incidence of seizures at doses of 400 mg daily as extended release tablets increases to 0.4%.

The incidence of seizures with bupropion depends on dose. Minimizing the risk of seizures includes restriction of total dosage to 400 mg daily as sustained-release. Administration of the daily dose in divided doses up to 150 mg twice daily, at least 8 hours apart, should minimize the risk of seizures.

Subjects will be cautioned not to take concomitant medications, whether prescription or over the counter (OTC) medications, or herbal supplements without consulting the site principal investigator or study physician.

These include:

- All antidepressants
- Neuroleptics
- Systemic corticosteroids
- Xanthines (i.e., theophilline, theophilline sodium glycinate and aminophylline)
- Medications that interfere with methamphetamine detection in urine samples (e.g. ephedrine and pseudoephedrine)

Subjects will be asked to inform a study physician, if they decide to use any smoking cessation products such as nicotine gum, nicotine patch, nicotine nasal spray or nicotine inhaler while on study. If any agents are used, blood pressure should be monitored closely as bupropion may increase blood pressure when used with these smoking cessation agents.

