11 TREATMENT PLAN

11.1 INVESTIGATIONAL AGENTS

Subjects assigned to receive bupropion SR will receive 150 mg every day for the first 3 days of treatment which will be increased to 300 mg daily (one tablet twice a day) for the duration of treatment until the final dose taper. The dose will be tapered to 150 mg every day for 3 days until termination or the last scheduled day of the 12-week treatment period. Subjects will be informed that they must taper the dose for three days before stopping the investigational agents completely in the event that they decide to terminate from the study prematurely. Subjects assigned to the

placebo group will receive matched placebo on the same schedule as the active treatment group. Subjects will be instructed to take study agents at least 8 hours apart when taking agents twice daily and not to take two tablets at once if a dose is missed. During the last 3 days of treatment during week 12 or before termination, subjects' investigational agents will be tapered down to 150 mg (or equivalent placebo) each day by taking only one tablet per day.

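### The clock windows in section 10.1 permit twice-daily doses as little as 6 hours apart, shorter than the at-least-8-hour spacing the protocol states elsewhere

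*Protocol*

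**What the plan says.** Section 10.1 of the protocol gives subjects two clock windows. They are to "consume the morning dose between 8:00 and 10:00 a.m. and the evening dose between 4:00 and 6:00 p.m". It then leaves the choice of times within the windows to the individual case, and asks that each subject keep to the times chosen. The next sentence states that dividing the daily dose, with at least 8 hours between doses, should minimize the risk of seizures.

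Section 10.5, on safety, repeats the spacing. It begins "Administration of the daily dose in divided doses up to 150 mg twice daily" and says that such doses, taken at least "8 hours apart, should minimize the risk of seizures". Section 11.1 turns the spacing into an instruction: "Subjects will be instructed to take study agents at least 8 hours apart when taking agents twice daily".

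Section 10.2 fixes when twice-daily dosing applies, through the tablets per day: "1 tablet on days 1-3 and days 82-84 and 2 tablets on days 4-81".

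**The concern.** The windows and the interval govern the same thing, the time between the two daily tablets, but they do not describe the same set of schedules. Someone reading only the windows sentence could choose a late morning and an early evening time, stay inside both windows, and have less than 8 hours between doses.

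What is at stake is participant safety as the protocol itself frames it. Section 10.5 ranks a lowered seizure threshold among the potentially gravest adverse effects of the drug and names the spacing as a way to limit the risk. Exclusion criteria 2 and 3 in section 9.2 also concern seizure history and drugs that lower the threshold. A timing rule that admits schedules outside the protocol's own safeguard leaves site staff and subjects to notice the mismatch and resolve it. The request for constant times means that a short pair, once chosen, would tend to persist.

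**Working it through.** **Inputs**

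- Morning window 8:00 to 10:00 and evening window 16:00 to 18:00 (section 10.1).
- Times may differ between subjects but should stay the same for each subject (section 10.1).
- Stated spacing of at least 8 hours (sections 10.1, 10.5 and 11.1).
- Two tablets per day on days 4 to 81 (section 10.2).

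**Range of daytime gaps**

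Gap = evening time − morning time.

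- Shortest: earliest evening − latest morning = 16:00 − 10:00 = 6 hours.
- Longest: latest evening − earliest morning = 18:00 − 8:00 = 10 hours.

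The windows therefore do not reproduce the stated minimum of 8 hours. Their shortest gap is 8 − 6 = 2 hours below it.

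**Overnight gap**

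Gap = 24 hours + next morning time − evening time.

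- Shortest: 24 + 8 − 18 = 14 hours.
- Longest: 24 + 10 − 16 = 18 hours.

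The overnight gap always exceeds 8 hours, so only the daytime gap is in question.

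**By morning time**

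| Morning dose | Shortest gap the windows allow (16:00 − morning) | Earliest evening time giving 8 hours (morning + 8) |
|---|---|---|
| 8:00 | 8.0 h | 16:00 |
| 8:30 | 7.5 h | 16:30 |
| 9:00 | 7.0 h | 17:00 |
| 9:30 | 6.5 h | 17:30 |
| 10:00 | 6.0 h | 18:00 |

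Two things follow. Every morning time has a permitted evening time that meets the spacing, because the windows are equally wide and start 8 hours apart. But only a morning dose at exactly 8:00 meets it at every permitted evening time, and a 10:00 dose meets it only at 18:00. In between, compliance depends on which evening time goes with the chosen morning time, and section 10.1 sets no such link.

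**How long a short pair could last**

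Days 4 to 81 inclusive: 81 − 4 + 1 = 78 days. On the single-tablet days (1-3 and 82-84) no second dose is due.

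**The case against.** The strongest reply is that the windows and the interval are cumulative conditions. The spacing stands in the same paragraph as the windows, and section 11.1 says that subjects are told it. A subject who follows the whole protocol picks a pair that meets both, such as 8:00 and 16:00 or 10:00 and 18:00, and has no gap under 8 hours. Only section 11.1 is worded as an instruction; sections 10.1 and 10.5 describe what the spacing should achieve.

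Most of this stands, and it rules out several stronger readings that a reader might infer.

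- *That the instructions cannot both be followed.* They can, as the table shows.
- *That subjects are told only the windows.* Section 11.1 says the opposite, and section 10.1 promises thorough instruction on taking the study agent.
- *That the windows sentence lets a subject's times drift from day to day.* It allows differences between subjects and asks for constancy within each one.
- *That the windows cause short gaps to go unrecorded.* A gap under 8 hours departs from section 11.1 whatever the windows say. The compliance procedures in sections 10.4 and 13.6.30 describe amounts and use of tablets, not clock times, but that would be so under any wording of the windows and is a separate matter.
- *That a given share of subjects would dose too close together.* The protocol gives no distribution of chosen times, and any share computed from the windows alone would ignore the section 11.1 instruction. It would describe the geometry of the windows, not expected exposure.

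What the reply does not remove is that section 10.1, as a stated rule on dosing times, admits pairs that section 11.1 forbids, with no text linking the second time to the first.

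**Conclusion.** The point holds as an inconsistency between stated rules. The windows in section 10.1 permit gaps of 6 to 10 hours, while the protocol elsewhere states at least 8. The 6-hour figure is the shortest permitted gap, not a typical one, and it rests on clock arithmetic alone. The possible duration of 78 days assumes that a subject settles on a short pair and keeps it as section 10.1 asks; the protocol does not say how likely that is.

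The documents support neither a claim that compliance is impossible nor a claim of excess seizures. No endpoint, sample size or analysis is affected. The point deserves correction because the protocol itself ties the spacing to seizure risk and because the correction is small.

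**What to change.** The sponsor, with the medical monitor, should reconcile sections 10.1, 10.5 and 11.1 so that every pair of times the windows permit also meets the interval the protocol states. The reconciled wording should be used in the subject instructions. How the passages are brought into line is a clinical decision for them; no time, interval or dose is proposed here.

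The cost is about one sentence of protocol text and the matching line in the subject instructions. Assessments, data collection and analysis do not change.

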10.2 LABELING

Investigational agents will be packaged in HDPE bottles with child-resistant closure with a 10day supply. The bottles will be labeled by Murty Pharmaceuticals with the drug name ("bupropion/placebo"), the random dose code, and the following statement – Caution: New Drug – limited by federal law to investigational use. Bottles will be distributed to investigational sites. When a subject is assigned to treatment, the local site research pharmacist, investigator or designee, will label the appropriate bottle based on the random dose code assigned to the patient with the following information: subject's study identification number, subject's letter identification code, the words "Study Week X", where X is the study week number (i.e., 1 through 12), and the number of tablets to take per day (i.e., 1 tablet on days 1-3 and days 82-84 and 2 tablets on days 4-81).

The label will also include a warning indicating that this medication should be kept out of children's reach. Special labels will be prepared for each site indicating the local Principal Investigator's name and 24-hour emergency telephone number.

10.3 STORAGE

Investigational agents will be stored at room temperature without exposure to direct sunlight in a secure location in the distributing pharmacy or at each investigator's facility.

10.4 RECORD OF ADMINISTRATION

Accurate recording of all investigational agent dispensing/administration will be made in the appropriate section of the CRF. On the first clinic visit of each week, subjects will be asked to return the bottle and all unused investigational agent. Unused study agent will be inventoried for discrepancies. Patients who have not been taking their tablets regularly will be encouraged to do so in the future. New, unused study agent (a 10-day supply) will then be dispensed to that patient. On each and all clinic visits (i.e. 3 times per week), self-reports of medication use since the last clinic visit will be recorded on the Treatment Compliance Study Drug Form.

10.5 SAFETY CONSIDERATIONS

One of the potentially most serious adverse effects of bupropion is reduction in the seizure threshold (Johnston *et al.*, 1991, Settle, 1998, Storow, 1994). Bupropion is contraindicated in

patients with a seizure disorder or a predisposing factor for seizures (e.g., cranial trauma history, current seizure disorder, concomitant use of drugs that lower seizure threshold). However, the relative risk of seizures with various antidepressants, including bupropion, has not been clearly defined and the incidence of seizures at doses of 400 mg daily as extended release tablets increases to 0.4%.

The incidence of seizures with bupropion depends on dose. Minimizing the risk of seizures includes restriction of total dosage to 400 mg daily as sustained-release. Administration of the daily dose in divided doses up to 150 mg twice daily, at least 8 hours apart, should minimize the risk of seizures.

Subjects will be cautioned not to take concomitant medications, whether prescription or over the counter (OTC) medications, or herbal supplements without consulting the site principal investigator or study physician.

These include:

- All antidepressants
- Neuroleptics
- Systemic corticosteroids
- Xanthines (i.e., theophilline, theophilline sodium glycinate and aminophylline)
- Medications that interfere with methamphetamine detection in urine samples (e.g. ephedrine and pseudoephedrine)

Subjects will be asked to inform a study physician, if they decide to use any smoking cessation products such as nicotine gum, nicotine patch, nicotine nasal spray or nicotine inhaler while on study. If any agents are used, blood pressure should be monitored closely as bupropion may increase blood pressure when used with these smoking cessation agents.

10.6 USED/UNUSED SUPPLIES

During the study, all investigational agents not used by the subject must be returned to the investigator for assessment of subject compliance. At the end of the study, all unused investigational agents must be inventoried. If any investigational agent is lost or damaged, its disposition should be documented. Unused investigational agents will be retained at Murty Pharmaceuticals until the end of the study.

11 TREATMENT PLAN

11.1 INVESTIGATIONAL AGENTS

Subjects assigned to receive bupropion SR will receive 150 mg every day for the first 3 days of treatment which will be increased to 300 mg daily (one tablet twice a day) for the duration of treatment until the final dose taper. The dose will be tapered to 150 mg every day for 3 days until termination or the last scheduled day of the 12-week treatment period. Subjects will be informed that they must taper the dose for three days before stopping the investigational agents completely in the event that they decide to terminate from the study prematurely. Subjects assigned to the

placebo group will receive matched placebo on the same schedule as the active treatment group. Subjects will be instructed to take study agents at least 8 hours apart when taking agents twice daily and not to take two tablets at once if a dose is missed. During the last 3 days of treatment during week 12 or before termination, subjects' investigational agents will be tapered down to 150 mg (or equivalent placebo) each day by taking only one tablet per day.

11.2 COGNITIVE BEHAVIORAL THERAPY

The CBT program will consist of thrice weekly, 90-minute group sessions through the 12-week trial. However, in order to help potential participants to stop methamphetamine use, they will be introduced to the counselors and scheduled to attend two 60-minute early recovery skills groups each week after signing informed consent up until study enrollment. Topics covered in this early recovery skills group include: Getting Rid of Paraphernalia; Triggers; Introduction to 12-Step Groups; and Brief Information on HIV (see Appendix II). Concepts presented in these sessions include the following: (1) self-monitoring and relapse analysis; (2) identification of "triggers" and cognitive strategies for coping with them; (3) teaching of problem solving skills; (4) education about methamphetamine and methamphetamine dependence; (5) education about HIV and reducing the risk of HIV transmission; and, (6) promotion of prosocial activities. The content of these group topics is prearranged and sequenced using a manualized format. This is a feasible treatment that is known to be well accepted by subjects and it represents an appropriate, ethically defensible standard treatment condition to serve as the "platform" for the medication trial. Staff members who provide CBT counseling will have attended training in the use of these materials. The CBT specialist will have a minimum of a master's degree (or equivalent) or a bachelor's degree plus counseling experience with substance users. To ensure that the integrity of these sessions is maintained, all sessions are audiotaped and reviewed centrally by the Principal Investigator or his designee. Our experience is that these sessions are valued by subjects and attendance is excellent. Thus, psychosocial involvement is seen as a standard or platform for the proposed pharmacotherapy evaluation.

12 STUDY PROCEDURES

12.1 SUBJECT RECRUITMENT

Interested candidates who are seeking treatment and are available to come to the clinic for 16-to-20 weeks will meet with the investigator or designated investigational staff and receive an explanation of the study purpose and requirements. If still interested after receiving an explanation of the study, the candidate will be given an opportunity to review, inquire about, and sign the informed consent form. If the study will be explained initially to the potential participant by investigational staff, a two-part consent form will be used with part one being consent to start screening procedures that do not include medical assessments such as blood collection and ECG. When an investigator or study physician has explained the study and answered the potential participants questions, part two of the consent form will be signed and the remaining medical procedures to be conducted during screening and baseline may be performed. Subjects are given a copy of the signed informed consent. Any participant who has difficulty understanding the information contained in the consent will be rescheduled and the consent process will be repeated. Research staff will work closely with the participant in an effort to help them understand the requirements of their participation. Persons with literacy problems will be assisted to the extent possible. Any participant who is unable to demonstrate understanding of the information contained in the informed consent will be excluded from study participation and assisted in finding other sources of treatment. Persons who are excluded, or who decline participation, will be given referrals to other resources in the area.

12.2 SCREENING/BASELINE ASSESSMENTS

After the subject has signed the informed consent form, the screening assessment process begins (which includes a two-week baseline assessment period). Assessments are described in section 12. Baseline assessments will occur over a two-week period. If a subject fails to provide a minimum of four completed MAWQ, at least four urine specimens – including one positive for urine methamphetamine and the accompanying other baseline repeated measures within the required two-week period, the baseline period may be shifted or extended until the subject meets the requirements in any consecutive 14-day period but within 4-weeks before randomization. Screening assessments are considered valid if the subject enrolls on the study within 4 weeks after consent is signed. If the subject does not meet the requirements within the 4 weeks, then screening/baseline measures must be repeated before subject enrollment but must not be started until 30 days have elapsed after the last screening visit. An End of Trial CRF must be completed if the subject is a screening failure.

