SAFETY ASSESSMENTS: All candidates for study enrollment will have a physical examination, a 12-lead electrocardiogram (ECG), and clinical laboratory studies (blood chemistry, hematology, and urinalysis performed during screening. If the potential participant is female, a pregnancy test will also be performed during screening, at study weeks 4 and 8, and at study termination. Vital signs, concomitant medication use, and a urine screen for other substances of abuse will be assessed weekly during treatment. AEs will be assessed at each visit. At study termination (the last assessment visit after treatment completion or if the subject terminates prematurely), subjects will be evaluated for AEs, vital signs, physical examination, clinical laboratory studies, and ECG.

EFFICACY ASSESSMENTS: The primary outcome response measures will be the weekly proportion of methamphetamine-free urines during the 12 weeks of treatment. Secondary assessments include analyses of other measures of success in the reduction of methamphetamine use including the proportion of successful subjects with 3 consecutive weeks of negative urine samples as measured by 9 consecutive negative urine samples for methamphetamine, proportion of methamphetamine non-use days by self report, the largest number of consecutive methamphetamine non-use days, and reductions in use as compared to baseline. Additional

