9.1 INCLUSION CRITERIA

Participants must:

- 1. Be males and/or females, between 18 and 65 years-of-age.
- 2. Have a DSM-IV diagnosis of methamphetamine dependence as determined by SCID.
- 3. Have at least 1 amphetamine or methamphetamine positive urine specimen (> 1000 ng/mL) within the two-week baseline period prior to randomization with a minimum of 4 samples tested.
- 4. Be willing and able to comply with study procedures.
- 5. Be able to verbalize understanding of consent form, able to provide written informed consent, and verbalize willingness to complete study procedures.
- 6. Be seeking treatment for methamphetamine dependence.
- 7. If female, have a negative pregnancy test and agree to use one of the following methods of birth control:
 - a. oral contraceptives
 - b. patch
 - c. barrier (diaphragm or condom) with spermicide or condom only
 - d. intrauterine progesterone or non-hormonal contraceptive system
 - e. levonorgestrel implant
 - f. medroxyprogesterone acetate contraceptive injection
 - g. surgical sterilization
 - h. complete abstinence from sexual intercourse

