- 10. Be mandated by the court to obtain treatment for methamphetamine-dependence where such mandate required the results of urine toxicology tests to be reported to the court.
- 11. In the opinion of the investigator, be expected to fail to complete the study protocol due to probable incarceration or relocation from the clinic area.
- 12. Be undergoing HIV treatment with antiviral and/or non-antiviral therapy.
- 13. Have AIDS according to the current CDC criteria for AIDS-MMWR 1999; 48 (no, RR-13:29-31).
- 14. Have CD4 (+) T-lymphocytes blood counts <500 cells/mm³.
- 15. Have known or suspected hypersensitivity to bupropion.
- 16. Be using bupropion or any medication that could interact adversely with bupropion, within the following times of beginning of administration of bupropion based on the longest time interval of A, B, and C, below or as otherwise specified:

- A) Five half lives of other medication or active metabolite(s), whichever is longer;
- B) Two weeks; or
- C) Interval recommended by other medication's product labeling.

Medications that fall into this category include:

- a. Bupropion (Wellbutrin[®], Zyban[®]) used during the past 30 days
- b. All antidepressants
- c. Neuroleptics
- d. Systemic corticosteroids
- e. Xanthines, i.e., theophilline, theophilline sodium glycinate and aminophylline
- 17. Have participated in any experimental study within 8 weeks (the nature of excluded studies may be discussed with NIDA investigators).
- 18. Be pregnant or lactating.
- 19. Have clinically significant laboratory values (outside of normal limits), in the judgment of the investigator (Appendix I).
- 20. Have active tuberculosis (positive tuberculin test and confirmatory diagnostic chest x-ray).
- 21. Have a diagnosis of adult (i.e., 21 years or older) asthma, or chronic obstructive pulmonary disease (COPD), including those with a history of acute asthma within the past two years, and those with current or recent (past 3 months) treatment with inhaled or oral beta-agonist or steroid therapy (because of potential serious adverse interactions with methamphetamine).

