12.3 SUBJECT ENROLLMENT AND RANDOMIZATION

If the prospective subject meets all of the study inclusion criteria, does not meet the exclusion criteria (a checklist will be provided in the CRFs), and has signed the informed consent form, then the subject can be enrolled onto the study. Investigators or study coordinators will submit a subject randomization form to KAI to receive the subject's random dose code number. The randomization form will contain all information pertinent to the stratification variables for treatment assignment. The KAI will then return to the site, a random dose code number, which assigns the participant to a dose level.

If any subject does not actually receive any investigational agent after they have been randomized, they are considered to be a randomization failure. A randomization failure notification will be submitted to KAI.

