12.4 TREATMENT PHASE

At the first clinic visit, subjects will be given instructions on how to administer the investigative agent, Bupropion or placebo, and will be given a one-week supply. This is a double-blind study in which neither the subject nor the site staff will know if the subject is receiving the investigational drug or the placebo. The subject will be given the first dose of the investigational agent in the clinic regardless of the time and will be observed for one hour to monitor for immediate adverse symptoms.

Subjects will be scheduled for treatment and assessment visits three times per week usually on a Monday, Wednesday, and Friday for 12 weeks. Two consecutive days may be scheduled around

holidays or other schedule conflicts. All subjects will be offered an opportunity for HIV testing and counseling and HIV/AIDS education (Appendix II). All subjects will be provided with CBT three times per week during the 12 weeks of treatment. Clinical evaluations are described in detail in section 12.

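### The protocol lets study drug start on a pregnancy test about 14 days old (28 in a corner case), because the 4-week screening validity rule covers the test and none is required at enrolment or before first dose

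*Protocol*

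**What the plan says.** Inclusion criterion 7 (section 9.1) reads: "If female, have a negative pregnancy test and agree to use one of the following methods of birth control". It gives no date or maximum age for the result. Under exclusion criterion 18 (section 9.2), participants must not "Be pregnant or lactating".

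The synopsis gives the schedule for women: "a pregnancy test will also be performed during screening, at study weeks 4 and 8, and at study termination". Section 13.1 lists the assessment once among the screening items. Table 1 marks it once in a combined Screening/Baseline column running from week -4 to week 0. Sections 13.3 and 13.4 agree on weeks 4 and 8 and termination. Section 13.6.13 describes a urine test for every female subject and gives no timing.

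Section 12.2 fixes how long a screening result lasts: "Screening assessments are considered valid if the subject enrolls on the study within 4 weeks after consent is signed". If urine or other baseline requirements are not met in two weeks, "the baseline period may be shifted or extended until the subject meets the requirements", within a 4-week limit.

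Section 12.3 says that once the criteria are met and consent is signed, "then the subject can be enrolled onto the study". Section 12.4 says: "The subject will be given the first dose of the investigational agent in the clinic regardless of the time". Neither asks for a pregnancy test, and the baseline list in 13.2 does not include one.

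**The concern.** Criteria 7 and 18 exist to keep pregnant women off study drug. A negative urine test describes the day it was taken, less the period in which a new pregnancy is too early to detect. The 4-week rule treats it like a screening result that changes slowly. This is more than a missing detail: the protocol states a validity period, and that period works against its own eligibility criteria.

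At stake is unintended fetal exposure. A woman who conceived after an early screening test can satisfy the eligibility form, be randomised and take study drug until the week 4 test, provided she attends it. Section 15.7 reports a dropout rate of 46% to 50% in the first fifty subjects, so attendance is not assured. Nothing here touches the primary outcome or its analysis.

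**Working it through.** The protocol gives no figure of its own to reproduce. The check is calendar arithmetic, then a rough bound on the benefit.

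**Inputs from the protocol**
- Standard baseline: 14 days (13.2). Screening may extend to 4 weeks, or 28 days (8.1, 12.2).
- Visits: three per week, usually Monday, Wednesday and Friday (12.4, 13.3).
- First on-treatment test: week 4, by preference at that week's first visit (13.3).
- Sample: 150 subjects, with a target of at least 30% women (section 9). Treatment lasts 12 weeks, or 84 days.

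**Assumptions not in the protocol**
- Conception rate constant at 0.5% to 3% per 4 weeks; all women fertile; half on bupropion.
- Urine hCG latency L of 10 to 14 days.
- Study weeks counted from first dose on day 1; first dose on the enrolment day.

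**Age of the result at first dose (T), with the test at the start of screening**
- Standard: T = 14 days.
- Corner case: T = 28 days. The protocol sets no maximum delay from enrolment to first dose, so any delay adds to this.

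**First dose to next test**
- Week 4 is days 22 to 28. Its first visit is day 22, which is 21 days after first dose.
- With a Monday start, the last visit of week 4 is day 26 (25 days after first dose). With a Wednesday or Friday start it is day 27 (26 days after).
- Range: 21 to 26 days.

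**Interval between the two tests**
- Standard: 14 + 21 = 35 to 14 + 26 = 40 days.
- Corner case: 28 + 21 = 49 to 28 + 26 = 54 days.
- With a test on the day of first dose: 21 to 26 days. In the standard case this removes 14/40 = 35% to 14/35 = 40% of the interval.

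**Bupropion-exposed pregnancies avoided**
- Women: 150 × 0.30 = 45.
- A test T days before dosing detects conceptions earlier than day -(T + L). A test at dosing detects those earlier than day -L. The extra window is T days, whatever L is.
- Avoided = 45 × rate × T/28 × 0.5.
- Standard: 45 × 0.005 × 14/28 × 0.5 = 0.056 to 45 × 0.03 × 14/28 × 0.5 = 0.338.
- Corner case applied to every woman: 45 × 0.005 × 28/28 × 0.5 = 0.113 to 45 × 0.03 × 28/28 × 0.5 = 0.675.

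**What the test would not catch**
- Too early to detect at first dose: 45 × 0.005 × 10/28 × 0.5 = 0.04 to 45 × 0.03 × 14/28 × 0.5 = 0.34.
- Conceived during treatment, ignoring dropout: 45 × 0.005 × 84/28 × 0.5 = 0.34 to 45 × 0.03 × 84/28 × 0.5 = 2.03.
- Share of all bupropion-exposed conceptions avoided, T/(T + L + 84): standard 14/112 = 12.5% to 14/108 = 13.0%; corner case 28/126 = 22.2% to 28/122 = 23.0%.

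**The case against.** The strongest reply is that nothing is misstated or contradictory. The synopsis, 13.1, 13.3 and 13.4 agree on the schedule, the 4-week window is bounded, and a screen older than that must be repeated. Criterion 18 excludes a state, not a dated result, and section 13.6.17 requires an eligibility form before randomisation. Contraception is mandatory and is checked under 13.6.5, and a positive test is a listed reason for termination in 12.12.1. A site may test late in the window, and an operations manual (section 16), not available here, may say more.

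The consistency of the schedule stands: this is a design choice that could be better, not a contradiction. The safeguards do not close the gap. An old negative satisfies the eligibility form, contraception lowers the rate but does not date the test, and termination acts only once a test is done. No text in the protocol requires a recent one.

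The stronger readings that a reader might infer do not hold:
- **That dosing on a 28-day-old result is the norm.** It needs a test on the consent day and enrolment on the last permitted day. Section 12.1 separates the parts of consent, so that only after the second part "the remaining medical procedures to be conducted during screening and baseline may be performed". Extension applies only when requirements are not met in two weeks. These ages are what is permitted, not what is typical.
- **That a test at first dose closes most of the gap.** In the standard case it removes 35% to 40% of the interval between tests and about 13% of exposed conceptions.
- **That the wait after first dose reaches 27 days.** On the usual schedule the last week 4 visit falls 25 or 26 days after first dose; 27 needs an off-schedule visit.

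**Conclusion.** The point holds as a small, cheap safety improvement. The 4-week rule in 12.2 permits study drug to start on a negative pregnancy test about 14 days old in standard screening and about 28 days old in the corner case, with no further test for about 21 to 26 days.

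The benefit of closing this is at most about 0.06 to 0.34 bupropion-exposed pregnancies over the whole trial in the standard case. That is an upper bound. It assumes every woman is tested at the start of screening and is fertile, although sterilised and abstinent women and women up to 65 are admitted. The conception rate is an assumption, not a protocol figure. The case for change rests on the kind of harm and the very low cost, not on the expected count.

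**What to change.** Exempt the pregnancy test from the 4-week validity rule in 12.2. Require a negative on-site urine test at the last visit before first dose, or on the day of first dose before dosing. Add matching lines in 12.3, 12.4, 13.2 and Table 1.

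The cost is a few protocol and CRF lines and at most about 45 extra dipsticks. Urine is already collected three times a week during baseline, section 13.6.14 already specifies the on-site device, and the first dose is already given in the clinic, so no visit is added. The week 4 and week 8 tests should stay, since they remain the check on early pregnancies missed at first dose and on conceptions during treatment.
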